#### 4.2 SCIENTIFIC RATIONALE FOR STUDY DESIGN

We seek to compare the Relief stent to our currently used ureteral stent to determine if it offers improved clinical outcomes. To this end, patients will be randomized to receive either the Relief stent or the standard stent and the prospectively collected data will be analyzed and compared. At our target enrollment of 50 patients (25 patients in each arm), a power analysis for our primary endpoint (differences in incidence of retrograde urine reflux between randomized study arms) determined that our study will be sufficiently powered (80%) to detect a moderate effect size ( $w = 0.4$ ) at an alpha level of 0.05.

#### 4.3 END OF STUDY DEFINITION

A participant is considered to have completed the study if he or she has completed all phases of the study including the last visit or the last scheduled procedure shown in the Schedule of Activities (SoA), Section 1.3.

The end of the study is defined as completion of the last visit or procedure shown in the SoA in the trial globally.

## 5 STUDY POPULATION

### 5.1 INCLUSION CRITERIA

To be eligible to participate in this study, an individual must meet all the following criteria:

1. Has capacity to consent
2. Stated willingness to comply with all study procedures and availability for the duration of the study
3. Persons, 18 years of age or older
4. Male or female subjects with confirmed ureteral and/or renal stones or strictures documented via abdomen X-ray KUB (kidney ureter bladder) or CT (computed tomography)

### 5.2 EXCLUSION CRITERIA

An individual who meets any of the following criteria will be excluded from participation in this study:

1. Distal ureteral obstruction where suture portion of stent may be placed
2. Urinary reflux (assessed by pre-stent cystogram)
3. Pregnancy or lactation
4. Patients requiring bilateral surgical stone management procedure
5. Infected stones
6. Patients where 24cm or 26cm stent lengths are not suitable
7. Ureteral structure in distal third of ureter
8. Intraoperative exclusion: based on urologist's discretion, if trauma has been induced to the distal ureter due to ureteroscopy maneuvers, exclude these patients

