## 4 STUDY DESIGN

### 4.1 OVERALL DESIGN

Allocation: Randomized 1:1 RELIEF stent vs. DJ Stent

Endpoint Classification: Comparison Study

Intervention Model: Two Group Assignment

Masking: Open Label

Primary Purpose: Treatment

Patients will undergo their scheduled ureteroscopy with laser lithotripsy and ureteral stent placement per standard of care methods.

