#### Day 0 (Stent Placement)

- Patients will be randomized to one of two study groups (Relief stent vs DJ stent)
- Medical charts will be reviewed and medications will be reviewed prior to surgery
- Stent will be placed per standard of care
- A intraoperative photo of the stent will be taken to confirm placement

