## 6 STUDY INTERVENTION

### 6.1 STUDY INTERVENTION(S) ADMINISTRATION

### 6.1.1 STUDY INTERVENTION DESCRIPTION

The study intervention is placement of the RELIEF Ureteral Stent, and the control product is the Ascerta stent by Boston Scientific. Placement of the stent is described in section 4 of the protocol.

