## 6.2 PREPARATION/HANDLING/STORAGE/ACCOUNTABILITY

### 6.2.1 ACQUISITION AND ACCOUNTABILITY

The Relief stent is provided from the company at no charge. The control stent is our current standard stent (Ascerta by Boston Scientific) which is available in stock. Both will be kept in an OR storage location, and the Relief stent will have a notice that it is for research purposes and not to be used outside of this study and without instruction by the study PI and coordinator.

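### The plan does not keep the allocation concealed until the discretionary intraoperative exclusion (criterion 8) is decided, so in this open-label trial it could be applied with the arm known

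*Combined protocol and SAP*

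**What the plan says.** - **Criterion 8 (section 5.2).** It is labelled an intraoperative exclusion at the urologist's discretion: "if trauma has been induced to the distal ureter due to ureteroscopy maneuvers, exclude these patients". Trauma is not defined further.
- **One operation (section 4.1).** "Patients will undergo their scheduled ureteroscopy with laser lithotripsy and ureteral stent placement per standard of care methods". Ureteroscopy and stenting belong to the same scheduled procedure, so criterion 8 can be judged only shortly before the stent goes in.
- **Masking (section 4.1).** "Masking: Open Label".
- **Day 0 list (section 4.1).** Section 6.1.1 sends the reader here: "Placement of the stent is described in section 4 of the protocol". The first bullet is randomization. The second is "Medical charts will be reviewed and medications will be reviewed prior to surgery". Stent placement follows. The list does not mention ureteroscopy or criterion 8 and gives no clock times. The schedule in section 1.3 places randomization on Day 0 and says no more.
- **Randomization (section 6.3).** The sequence is generated by computer and patients are allocated from it. The section does not say who holds the sequence, whether it is concealed, or when the arm is disclosed.
- **Stent control (section 6.2.1).** The RELIEF stent is "not to be used outside of this study and without instruction by the study PI and coordinator". No time is set for that instruction.
- **After randomization (section 7.2).** The investigator may withdraw a participant found to meet an exclusion criterion that had not been recognized. A participant who is randomized but does not receive the intervention may be replaced. The reason for withdrawal goes on a case report form.
- **Screen failures (section 5.4).** These are consented participants who are not then randomly assigned or entered.

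**The concern.** Random allocation makes the arms comparable only if the decision on who stays in the trial is made without knowledge of the arm. Criterion 8 is a judgement without an objective threshold, made by the operator, at a moment when the arm may already be known. The unused slot may then be filled by another patient.

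If the threshold for calling trauma shifts with the assigned stent, the two arms will hold different kinds of patient. It need not shift deliberately: an operator might be more cautious about a distal ureter that is to receive an unfamiliar device. The primary comparison is the incidence of reflux with 25 patients per arm, so a handful of selective exclusions is a visible fraction of an arm. No later analysis can restore the comparability lost this way.

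**Working it through.** **1. Can criterion 8 fall after the arm is known?**

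| Question | What the plan gives |
|---|---|
| When can criterion 8 be judged? | During ureteroscopy (5.2) |
| When is the patient randomized? | Day 0 (1.3); first bullet, ahead of a step done before surgery (4.1) |
| Is the allocation hidden until criterion 8 is settled? | Not stated (4.1, 6.2.1, 6.3) |
| Can the patient leave after randomization and be replaced? | Yes, if the intervention was not received (7.2) |

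Taken in the listed order, randomization comes before ureteroscopy and so before criterion 8. The list does not claim to be a timed sequence, so this is a permitted course and not a stated one. Section 5.4 closes the gap only if the patient has not yet been randomized, which is the open question.

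**2. The plan's own figure.** Section 9.2 gives 80% power for N = 50, w = 0.4 and alpha 0.05. The noncentrality is 50 × 0.4² = 8. With 1 degree of freedom and critical value 3.841, power is 0.807, so the figure reproduces. This point does not change it. For scale, w = 0.4 corresponds to a difference of 2 × 0.4 × √(p(1 − p)), where p is the average reflux rate. That is 40 points at p = 0.5 and 32 points at p = 0.2 or 0.8.

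**3. Illustration of size. All rates are assumed.** The plan gives no trauma rate, no reflux rate and no link between them. Take no true stent effect, reflux p = 0.5 overall, trauma in a fraction f of patients, reflux rate pH among them, and a fraction e of them excluded from the RELIEF arm only, with none excluded from the control arm.

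- Reflux without trauma: pL = (p − f·pH)/(1 − f)
- Trauma share left in the RELIEF arm: f2 = f(1 − e)/(1 − f·e)
- Reflux rate in that arm: f2·pH + (1 − f2)·pL
- Bias = p − that rate (positive favours RELIEF)

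Worked extreme: f = 0.20, e = 1, pH = 0.9. Then pL = (0.5 − 0.18)/0.8 = 0.40, f2 = 0, and the bias is 0.5 − 0.4 = 0.10.

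Bias in percentage points:

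| pH | f .10, e .5 | f .10, e 1 | f .15, e .5 | f .15, e 1 | f .20, e .5 | f .20, e 1 |
|---|---|---|---|---|---|---|
| 0.3 | −1.1 | −2.2 | −1.6 | −3.5 | −2.2 | −5.0 |
| 0.5 | 0 | 0 | 0 | 0 | 0 | 0 |
| 0.7 | 1.1 | 2.2 | 1.6 | 3.5 | 2.2 | 5.0 |
| 0.9 | 2.1 | 4.4 | 3.2 | 7.1 | 4.4 | 10.0 |

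The size is 5 points or less in 22 of 24 cells. Expected exclusions are 25·f·e, which runs from 25 × 0.10 × 0.5 = 1.25 to 25 × 0.20 × 1 = 5. The sign reverses if the control arm loses the patients instead.

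**4. Effect on the test.** Exact binomial enumeration, two-sided 0.05, 25 v 25 after replacement, control rate 0.5:

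| Bias | Fisher | Chi-square (uncorrected) |
|---|---|---|
| 0 | 3.3% | 6.5% |
| 5 points | 4.4% | 8.1% |
| 10 points | 7.8% | 13.1% |

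The 6.5% with no bias comes from the discreteness of the test and not from this defect.

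**The case against.** The strongest reply is that the harm depends on an order the plan never states. Randomization sits in the stent-placement column of the schedule and not at screening, criterion 8 is listed as an eligibility exclusion, and section 5.4 fits exclusion before allocation. The Day 0 bullets omit ureteroscopy altogether and look more like a task list than a sequence. Nor does open label mean that the operator knows the arm before ureteroscopy is over.

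All of that stands. A reader might infer that the plan randomizes patients before surgery and so exposes the arm to the urologist before criterion 8 is decided, or that biased exclusion has been shown. The documents support neither: they fix the day and leave the order and the reveal open. But the benign order is not stated either, and a site could follow the text as written and exclude with the arm known.

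The second reply is that the effect is small. Every rate in the illustration is assumed, the exclusions are put in one arm only, and the bias is zero if trauma patients reflux at the average rate. At 5 points Fisher's test still rejects less than 5% of the time. This also stands, and it limits how serious the point is. It does not remove the point, because the true rates are unknown and the route can be closed cheaply.

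Third, the withdrawal form makes such exclusions traceable. That helps detection but does not prevent them, and nothing requires them to be reported by arm.

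Section 10.1.8 mentions a Manual of Procedures, which might cover the reveal. It was not available for this check, and neither was section 10.1.4.

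**Conclusion.** The point holds as a gap in allocation concealment: a discretionary exclusion during surgery, an open-label design, no stated concealment or time of reveal, and a replacement rule. Together these let a site following the listed Day 0 order exclude and replace patients with the arm known. It should be fixed.

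The size and direction of any bias are not derivable from the plan. The illustrative range is 0 to 10 points in either direction, against a design difference of 40 points at 50% average reflux. It rests on assumed trauma in 10% to 20%, half to all of those patients excluded from one arm only, and reflux of 30% to 90% among them. The 10-point figure needs all the extreme assumptions at once.

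**What to change.** State in sections 4.1 and 6.3 and in the schedule of activities that the allocation is concealed, and that it is assigned or revealed in the operating room only after the criterion 8 decision has been documented, just before the stent is opened. Patients excluded before that moment are then screen failures under section 5.4. Any eligibility exclusion that still occurs after randomization should be reported by arm with its reason. How trauma is judged and managed stays with the investigators.

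The cost is protocol wording and one reveal step in the operating room. Both stents must be at hand for each case, which section 6.2.1 already provides for: "Both will be kept in an OR storage location". The target of 25 per arm and the planned tests do not change. More patients must consent than are randomized: 50/0.9 ≈ 56 to 50/0.8 = 62.5, so 63, if criterion 8 removes an assumed 10% to 20%.

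A ban on replacement is not part of this change. It would reduce N whenever an exclusion did follow randomization (power 0.765 at N = 45 and 0.716 at N = 40, by the section 9.2 calculation), and the late reveal already removes the cause. Section 9.3 restates the inclusion criteria and defines no analysis set. That is a separate matter, and defining one would not cure this defect.

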### 5.3 LIFESTYLE CONSIDERATIONS

N/A

### 5.4 SCREEN FAILURES

Screen failures are defined as participants who consent to participate in the clinical trial but are not subsequently randomly assigned to the study intervention or entered in the study. A minimal set of screen failure information is required to ensure transparent reporting of screen failure participants, to meet the Consolidated Standards of Reporting Trials (CONSORT) publishing requirements and to respond to queries from regulatory authorities. Minimal information includes demography, screen failure details, eligibility criteria, and any serious adverse event (SAE).

Individuals who do not meet the criteria for participation in this trial (screen failure) because of a stent contraindication may be rescreened. Rescreened participants should be assigned the same participant number as for the initial screening.

## 6 STUDY INTERVENTION

### 6.1 STUDY INTERVENTION(S) ADMINISTRATION

### 6.1.1 STUDY INTERVENTION DESCRIPTION

The study intervention is placement of the RELIEF Ureteral Stent, and the control product is the Ascerta stent by Boston Scientific. Placement of the stent is described in section 4 of the protocol.

## 6.2 PREPARATION/HANDLING/STORAGE/ACCOUNTABILITY

### 6.2.1 ACQUISITION AND ACCOUNTABILITY

The Relief stent is provided from the company at no charge. The control stent is our current standard stent (Ascerta by Boston Scientific) which is available in stock. Both will be kept in an OR storage location, and the Relief stent will have a notice that it is for research purposes and not to be used outside of this study and without instruction by the study PI and coordinator.

### 6.2.2 FORMULATION, APPEARANCE, PACKAGING, AND LABELING

Both the Relief stent and control stent are supplied in standard sterile packaging.

### 6.2.3 PRODUCT STORAGE AND STABILITY

The stents will be stored in the usual location where Urology disposable products are kept.

### 6.2.4 PREPARATION

No preparation is required.

## 6.3 MEASURES TO MINIMIZE BIAS: RANDOMIZATION AND BLINDING

Patients will be randomized to receive either the Relief stent or the standard ureteral stent. The randomization sequence will be computer-generated, and patients will be randomly allocated based on this sequence.

## 6.4 STUDY INTERVENTION COMPLIANCE

There will be three questionnaires completed by subjects at multiple different timepoints which will ensure study intervention compliance.

## 6.5 CONCOMITANT THERAPY

N/A

## 7 STUDY INTERVENTION DISCONTINUATION AND PARTICIPANT DISCONTINUATION/WITHDRAWAL

### 7.1 DISCONTINUATION OF STUDY INTERVENTION

Discontinuation from having the stent placed for the expected duration of 7-14 days does not mean discontinuation from the study, and remaining study procedures should be completed as indicated by the study protocol. If a clinically significant finding is identified (including, but not limited to changes from baseline) after enrollment, the investigator or qualified designee will determine if any change in participant management is needed. Any new clinically relevant finding will be reported as an adverse event (AE).

The data to be collected at the time of study intervention discontinuation will include the following:

- Detailed reason for early or late stent removal

## 7.2 PARTICIPANT DISCONTINUATION/WITHDRAWAL FROM THE STUDY

Participants are free to withdraw from participation in the study at any time upon request.

An investigator may discontinue or withdraw a participant from the study for the following reasons:

- Pregnancy
- Significant study intervention non-compliance
- If any clinical adverse event (AE), laboratory abnormality, or other medical condition or situation occurs such that continued participation in the study would not be in the best interest of the participant
- If the participant meets an exclusion criterion (either newly developed or not previously recognized) that precludes further study participation

The reason for participant discontinuation or withdrawal from the study will be recorded on the Withdrawal Case Report Form (CRF). Research participants who sign the informed consent form and are randomized but do not receive the study intervention may be replaced. Research participants who sign the informed consent form, and are randomized and receive the study intervention, and subsequently withdraw, or are withdrawn or discontinued from the study, will not be replaced.

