**Study Endpoints:****1- Primary effectiveness endpoint:**

- Study success defined as adequate short-term drainage defined as the presence of the stent in the ureter and the lack of surgical or other intervention to treat symptoms associated with the stent itself on the stented side during the first 48 hours [Day 0-2] following placement.
- [Note: In some cases, the ureteral stent may not be sufficient to relieve pain (not associated with stent specifically) and alternative surgical treatment may be warranted. In these cases, patient data will be captured but non-device related cause captured as reason for subject stenting termination.]
- Assessment of retrograde urine reflux after placement of the ureteral stent, as determined by the visualization of urine in the distal ureter to the kidney using cystography after contrast gravity-filling of the bladder and assigning a urinary reflux grade based on:
  - Grade I: urine refluxes into the ureter only.
  - Grade II: urine refluxes into the ureter and up to the kidney without dilation.

- Grade III: urine refluxes into the ureter and kidney and causes mild dilation.
- Grade IV: urine refluxes into ureter and kidney and causes dilation without twisting of the ureter.
- Grade V: urine refluxes into ureter and kidney and causes significant dilation with twisting of the ureter.

- Visualization of distal coil in bladder, after stent placement. Document placement using a cystoscope.

2- Primary safety endpoint:  
Assessment of pain or irritative symptoms (incidence, severity) attributed to the ureteral stent as well as unplanned return visits to ED, OR, or clinic.

3- Secondary endpoint:

- USSQ Scale (Ureteral Stent Symptoms Questionnaire) [Time Frame: Day 3 as endpoint]
- Unplanned hospital visits or doctor visits related to the stent
- Medication use endpoint:
  - Physicians can prescribe standard medications such as alpha blocker (Tamsulosin), Anticholinergic (Oxybutynin), phenazopyridine (Pyridium), ibuprofen and Tylenol prn pain for the duration of the stent plus 1 day (post stent removal) (Document on CRF)
  - Requests for “breakthrough” pain medication (narcotics) would be at the request of the patient post procedure (not to be given as a standard dose). (Document on CRF)
  - Patients to keep medication diary in situations where patients are not taking medications as prescribed

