#### 9.2 SAMPLE SIZE DETERMINATION

At our target enrollment of 50 patients (25 patients in each arm), a power analysis for our primary endpoint (differences in incidence of retrograde urine reflux between randomized study arms) determined that our study will be sufficiently power (80%) to detect a moderate effect size ( $\omega = 0.4$ ) at an alpha level of 0.05.

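### Section 7.2 allows unmasked withdrawal from the study for an adverse event or non-compliance, with no outcome collection afterwards, so symptom data can be lost for outcome-related reasons that differ by arm

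*Combined protocol and SAP*

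**What the plan says.** Section 4.1 sets out the design: "Allocation: Randomized 1:1 RELIEF stent vs. DJ Stent" and "Masking: Open Label". Section 9.2 plans 25 patients per arm.

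Section 7.1 deals with a stent that does not stay in for its expected time. This "does not mean discontinuation from the study, and remaining study procedures should be completed as indicated by the study protocol". The reason for early or late removal is recorded.

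Section 7.2 deals with leaving the study. Among the grounds on which the investigator may withdraw a patient are "Significant study intervention non-compliance" and "If any clinical adverse event (AE), laboratory abnormality, or other medical condition or situation occurs such that continued participation in the study", the latter qualified by a judgement that staying in would be against the patient's best interest. The reason goes on a Withdrawal CRF. A patient who has received the intervention and is then withdrawn is not replaced. The section does not mention further outcome collection.

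Section 3 makes this the primary safety endpoint: "Assessment of pain or irritative symptoms (incidence, severity) attributed to the ureteral stent", together with unplanned return visits. The secondary endpoints are the Day 3 USSQ, unplanned stent-related visits and medication use.

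Section 9.3, headed as the analysis populations, repeats the inclusion criteria. Sections 9.4.1 to 9.4.4 give no missing-data rule. Intention-to-treat appears only in the abbreviation list.

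**The concern.** The device is placed once, on Day 0. In the Schedule of Activities, what follows is USSQ, medication review, adverse event review, removal per standard of care and a photo. For a patient who tolerates the stent badly, leaving the study therefore changes mainly what is measured. The symptoms that could prompt withdrawal are also the symptoms the trial compares.

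The person deciding knows the arm. Section 4.1 brings patients with unusual pain in for clinician evaluation, so the worst cases reach unmasked staff. Section 6.4 relies on questionnaires to ensure compliance, so a patient too unwell to complete the USSQ might be classed as non-compliant.

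If such patients leave one arm more than the other, the remaining scores make that arm look better tolerated than it was. The bias could favour either stent, and no stated analysis rule would correct or reveal it.

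**Working it through.** **The plan's own figure.** Section 9.2 gives N = 50, w = 0.4 and alpha = 0.05, and says "our study will be sufficiently power (80%) to detect a moderate effect size". For a chi-square test with 1 degree of freedom, the noncentrality is N × w² = 50 × 0.16 = 8, and power is 0.807. The stated 80% is reproduced and is not in dispute. It concerns reflux incidence; no symptom endpoint has a power statement.

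**Which rule applies to an intolerable stent.**
- Section 7.1: the stent comes out, the patient stays and the remaining procedures are done.
- Section 7.2: the same patient may be withdrawn from the study if the investigator judges that staying is not in the patient's interest, or finds significant non-compliance.
- No sentence says which section governs, or that contacts continue after a 7.2 withdrawal.

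**Which data are exposed.**
- *Triggering event:* kept. Section 8.3.4 has all adverse events documented and followed to resolution. The form in Section 8.2 records tests, therapies and clinical visits until then.
- *Later non-serious events:* partly exposed. Recording ends 7 days after the last day of participation. For withdrawal on Day 1 that is Day 1 + 7 = Day 8, and on Day 3 it is Day 10. For a completer (last contact Day 9–12) it is Day 16–19.
- *USSQ:* scores after withdrawal are lost. The Day 3 endpoint is lost only if withdrawal comes by about Day 3.
- *Routine medication tracking, later pain severity and later visits unrelated to the recorded event:* exposed.
- *48-hour drainage:* exposed only to withdrawal by about Day 2–3.
- *Reflux:* exposed only if cystography comes after withdrawal. The Schedule of Activities does not list post-stent cystography, so this cannot be shown.

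**Illustrative size.** The documents give no withdrawal rate. Assume a normal symptom score with SD 1, no true difference, 25 per arm, and the k worst scorers lost from one arm only, all before scoring.
- Standard error of the difference with full data: √(1/25 + 1/25) = √0.08 = 0.283 SD.
- Shift in the depleted arm: the mean of the lowest 25 − k of 25 normal values, found by simulation. A run of 200,000 samples gave −0.151, −0.215 and −0.335 for k = 2, 3 and 5. An independent run of 20,000 gave −0.152, −0.217 and −0.337.
- False-positive rate: Mann-Whitney test at two-sided 0.05, from the 20,000-sample run.

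| k lost | Shift (SD) | Shift ÷ 0.283 | False-positive rate |
|---|---|---|---|
| 0 | 0.00 | 0.00 | 4.7% |
| 2 | 0.15 | 0.53 | 8.4% |
| 3 | 0.22 | 0.78 | 11.4% |
| 5 | 0.34 | 1.20 | 21.1% |

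For a binary outcome, assume severe pain in 10 of 25 in each arm. Removing 3 severe cases from one arm leaves 7/22 = 32% against 40%. Removing 5 leaves 5/20 = 25% against 40%. The Fisher p-values are 0.76 and 0.35, so here the harm is to the estimate rather than to significance. If equal numbers of the worst scorers left both arms, the shifts would cancel on average under no true difference.

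**The case against.** The strongest reply is that the plan already handles most of this. Several stronger readings are tempting, and the documents do not support them.

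- *Any adverse event is enough for withdrawal.* It is not: the clause carries a best-interest condition. Since later participation is mostly contacts and questionnaires, stent pain should seldom meet it. That stands and lowers the likely frequency, but the judgement is still made by someone who knows the arm.
- *Sections 7.1 and 7.2 contradict each other.* Strictly they do not: one concerns the stent, the other study membership. What remains is that the same patient could be handled under either.
- *Adverse events, treatments and visits disappear.* The triggering event, with its therapies and visits, is still recorded, and Section 7.2 does not say that earlier data are discarded.
- *The powered comparison is weakened.* With 46 or 40 evaluable patients, power would be 0.774 or 0.716, but only if reflux results were lost, and nothing shows that they would be.
- *Bias of the tabulated size is to be expected.* Three of 25 is 12% of one arm withdrawn by the investigator before scoring, and exactly the worst scorers. That is a constructed extreme.

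It can also be said that a patient withdrawn for missing questionnaires has already lost those scores. That is true of past contacts but not of the remaining ones. The non-compliance route is a possibility, not something the documents show happening.

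**Conclusion.** The point holds as a design weakness of moderate weight. The stated rule permits unmasked withdrawal for reasons tied to the primary safety endpoint, provides for no later outcome collection, and is not offset by a defined analysis set or missing-data rule. The exposure lies mainly in USSQ scores, routine medication tracking, and later pain severity and visits.

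The worst case is about half to 1.2 standard errors of the between-arm difference for 2 to 5 patients. That rests on a normal score, loss of exactly the worst scorers, loss from one arm only, and loss before scoring. Less selective or more balanced loss would do less. The documents support that bias can arise, not that it will, and they do not indicate its direction. At 25 per arm, even a few such withdrawals would matter to the symptom comparison.

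**What to change.** Reconcile Section 7.2 with Section 7.1 by adding three statements:

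1. A patient withdrawn by the investigator for an adverse event, medical condition or non-compliance continues the scheduled USSQ, medication, unplanned-visit and adverse event contacts, by phone where suitable, unless the patient declines or cannot be reached.
2. Data already collected are kept.
3. These patients are analysed in the arm to which they were randomized.

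The third statement also belongs in Section 9.3.

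A reader might go further and make withdrawal of consent the only way follow-up can end. That is not needed: it would remove a participant-protection clause and the other withdrawal grounds, and would overlook loss to follow-up under Section 7.3. The investigator's discretion over clinical management and the other grounds stay as they are.

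The cost is a short amendment and a few extra contacts of a kind that Section 7.1 already requires after early stent removal. It should be in place before patients are withdrawn, because symptom scores not collected at the time cannot be recovered.
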